Specific Aim 1: Comparing effectiveness of high frequency and burst spinal cord stimulation in improving pain, function and pain interference in patients with chronic low back and/or leg pain persistent more than 6 months.

We hypothesize that high frequency spinal cord stimulation is more effective than burst spinal cord stimulation in decreasing chronic low back and/or leg pain.

Our primary outcome is change from baseline in pain intensity at 12 months. We will also compare improvement in function and pain interference at all follow up time points. We will plot the trend of all these measures and study change from baseline at 12 months. We will use repeated measure linear regression to compare these measures between the groups at follow up time points with time as the fixed effect and treatment as random effect.

Specific Aim 2: Comparing effectiveness of high frequency and burst spinal cord stimulation in improving depression and anxiety in patients with chronic low back and/or leg pain persistent more than 6 months.

We hypothesize that high frequency spinal cord stimulation is more effective than burst spinal cord stimulation in decreasing stress and anxiety in patients with chronic low back and/or leg pain.

Burst stimulation modulates medial thalamic pathway, which attributes adverse emotions to pain. We will therefore compare emotional response to these waveforms. We will compare change from baseline of depression and anxiety at 12 months. We will also plot depression and anxiety trend at all follow up time points between two groups using repeated measure linear regression. We will then perform a similar stratified analysis in responders (patients with 50% or more pain reduction at 1 year) and non-responders to these treatments; this analysis is to assess if pain reduction is an effect measure modifier in this relationship.

Research Strategy

(a) Background and Significance:

Chronic pain is a major healthcare problem affecting more than 100 million Americans. Chronic pain is a devastating disease entity that can significantly compromise patients' quality of life and cause disability. It imposes an annual cost of around \$635 billion on United States healthcare system. The number of treatment modalities available for this condition is disproportionately low; the quality of data available for these modalities is not optimal either.¹

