Primary Outcome:

- Change from baseline in pain intensity at 12 months. Baseline pain intensity is measured at last CHOIR completion before trial, and is based on patient reported outcome in CHOIR for average pain in the week prior to completion of questionnaire.

Secondary Outcomes:

1. Patient global impression of change at all follow up time points
2. Pain intensity at all follow up time points
3. Change from baseline in function at 12 months
4. Function at all follow up time points
5. Change from baseline in pain interference at 12 months
6. Pain Interference at all follow up time points
7. Change from baseline in depression at 12 months
8. Depression at all follow up time points
9. Change from baseline in anxiety at 12 months
10. Anxiety at all follow up time points
11. Daily opioid dose in morphine equivalent at all follow up time points

Analytic Plan: We will test the hypotheses that:

1. High frequency spinal cord stimulation is more effective than burst spinal cord stimulation in decreasing pain at 12 months in patients with chronic low back and/or leg pain.
2. High frequency spinal cord stimulation is more effective than burst spinal cord stimulation in improving pain, pain interference and function in patients with chronic low back and/or leg pain.

We will use repeated measure linear regression to compare these measures between the groups at follow up time points with time as the fixed effect and treatment as random effect. This method allows missing data subject to assumption of missing at random.

3. Burst spinal cord stimulation is more effective than high frequency spinal cord stimulation in improving depression and anxiety in patients with chronic low back and/or leg pain.

We will use repeated measure linear regression to compare these measures between the groups at follow up time points with time as the fixed effect and treatment as random effect. This method allows missing data subject to assumption of missing at random. Some improvement in depression and anxiety is expected to be the result of improvement in pain and function. We will also perform a stratified analysis in responders (patients who achieve >50% pain relief) and non-responders (patients who do not achieve 50% pain relief) to the treatments.

4. Patients receiving burst spinal cord stimulation will report higher satisfaction with treatment using patient global impression of change compared with patients receiving high frequency spinal cord stimulation.

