We will use SAS Enterprise Guide (SAS Institute Inc., Cary, NC) for all analyses. Our null hypotheses are similarity of measures. We will perform a two-sided hypothesis testing with accepted type I error of 0.05. We will compare baseline characteristics using t-test for continuous variables and chi-square for categorical variables. We will adjust for the variables that are different between the groups in our final regression model. Our primary analysis will be based on modified intention-to-treat. We will only exclude patients with no follow up data from our final analysis. We will then perform a secondary analysis based on implants only (excluding patients who do not achieve appropriate pain control in trial period).

We will then perform the following subgroup analyses:

1. Patients who have undergone lumbar spine fusion versus patients who have not.
2. Patients with back pain only (based on baseline body map) versus patients with back and leg pain or leg pain only.

3. Patients with PROMIS depression measure of above 90th percentile in baseline evaluation.
4. Patients with PROMIS anxiety measure of above 90th percentile in baseline evaluation.

The rate of CHOIR survey completion is more than 60% in our routine clinical care. We expect a higher rate for our proposed study considering that these surveys are abbreviated, and participants will receive more frequent reminders as well as telephone reminders (currently patients receive only one email reminder to complete the survey). For our primary outcome we will try to minimize missing data by calling the patients who do not complete the surveys up to seven times; we will try to ask and record the pain intensity even if they are not willing to complete surveys. Our analysis model will allow for missing data in longitudinal variables, subject to assumption of missing at random.

Data and Safety Monitoring Plan: We will not perform any interim analyses for benefit, harm or futility. We will establish a data and safety monitoring board consisting of investigators, at least two independent clinicians in our clinic (not part of the study team), and at least one neurosurgeon subspecialized in spine surgery who will monitor the study quarterly for adverse events and patient safety, reporting of adverse events, enrollment pace and study timeline, quality of data, and deviations from the protocol.

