Sample size: The highest standard deviation of NRS pain scale in our clinic is 2.25 based on prior publications.^{19,21-25} Accepting type I error of 0.05 with 80% power, we will require 80 participants per group to detect one unit between-group difference in change from baseline in NRS pain scale. We are proposing a more conservative (larger) sample size to preserve power considering that some patients do not proceed from trial to implant and do not receive therapy. Currently more than 80% of patients who undergo a trial of spinal cord stimulation proceed to receiving an implant. We will therefore target 100 patients in each arm. Correlation between repeated measure will decrease variance and increase the power of the proposed study.

Timeline: Stanford Pain Management Center performed more than 120 trial of spinal cord stimulation in 2017 and this practice is increasing in our division. We expect a high consent rate considering the nature of our study. We believe we will be able to complete recruitment in two years; thus, last follow up of last recruited patient will be completed by five years.

Data Management: CHOIR will be the main tool for data collection and storage for the study. At completion of the study, the data from CHOIR, participants' electronic health records and California Prescription Drug Monitoring Program will be downloaded for analysis. After initial steps of data preparation, we will de-identify the dataset for further analysis. The principal investigator will save the de-identification code on a secure computer within Stanford University Network only.

Limitations:

1. One of the most important advantages of pragmatic clinical trial with less stringent inclusion/exclusion criteria is to improve the ability to generalize the results to a wider range of patients. However, considering that the current study is a single center study conducted in a tertiary pain management center, our sample might not be representative of chronic pain patients seen by community pain providers.
2. Our aim is to integrate our trial into patient care; thus, we are not blinding the provider and the participants. Method of data collection is similar in both groups and does not involve interaction with investigators. This will minimize, but not eliminate, the bias introduced by proceeding with an open label design.

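### The only model with stated terms makes treatment a random effect, so it has no parameter for the month-12 difference between arms that the trial is meant to test

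*Combined protocol and SAP*

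**What the plan says.** The primary outcome is "Change from baseline in pain intensity at 12 months" (Outcomes, Primary Outcome). Hypothesis 1 of the Analytic Plan is directional: "High frequency spinal cord stimulation is more effective than burst spinal cord stimulation in decreasing pain at 12 months".

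The only model whose terms are spelled out compares the groups "at follow up time points with time as the fixed effect and treatment as random effect". The sentence stands under Specific Aim 1, directly after the description of the outcomes, and twice in the Analytic Plan, after hypotheses 2 and 3. Specific Aim 2 names repeated-measures linear regression without giving its terms.

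The rest of the Analytic Plan adds a null of similar measures and this testing rule: "We will perform a two-sided hypothesis testing with accepted type I error of 0.05". On covariates it says: "We will adjust for the variables that are different between the groups in our final regression model". The Sample size section sizes the trial "to detect one unit between-group difference in change from baseline in NRS pain scale" and adds: "Correlation between repeated measure will decrease variance and increase the power of the proposed study". No section names a treatment-by-visit term, a month-12 contrast within the model, a patient effect or a covariance structure.

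**The concern.** High frequency and burst are the two specific treatments being compared, not a sample from a population of treatments. Their mean difference is what hypothesis 1 asserts and what the sample size is built on. If treatment is random, that difference is not a parameter. The model returns a between-treatment variance estimated from two levels (1 degree of freedom), which has no sign and so cannot say which arm is better. It also returns a predicted arm difference shrunk towards zero. The plan names no test to apply to either quantity.

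Two further terms are missing. Without a treatment-by-visit term, any arm difference is an average over seven visits from month 1 to month 36, which can be larger or smaller than the month-12 effect. Without a patient term or within-patient covariance, repeated surveys from one patient count as independent, although the Sample size section relies on their correlation. At stake is whether the primary test has the promised two-sided 0.05 error rate and answers the month-12 question.

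**Working it through.** **Inputs from the document.** Two arms, 1:1 (Randomization); seven follow-up visits at months 1, 3, 6, 12, 18, 24 and 36 (Data Collection); two-sided 0.05 (Analytic Plan); SD 2.25, difference 1.0, power 80%, 80 per group, target 100 per arm (Sample size).

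**Assumptions, not in the document.** Equal correlation ρ of 0.3, 0.5 or 0.7 between any two visits; complete data; 80 per arm; no true difference. For random treatment, a REML likelihood-ratio test of the treatment variance with the 50:50 mixture cut-off of 2.706.

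**Step 1: the plan's own sample size.** n = 2 × [2.25 × (1.960 + 0.842) / 1.0]² = 79.5, rounded up to 80 per group. Allowing for 20% who do not reach implant, 80 / 0.8 = 100. Both stated figures reproduce. The formula is for a fixed difference between two means. At 80 per group the power is 79.8% by the t-test (80.3% by the normal approximation).

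**Step 2: treatment random, one time point.** For F > 1 the likelihood-ratio statistic is (d + 1) ln[(d + F)/(d + 1)] − ln F, where d is the error degrees of freedom. With d = 2 × 80 − 2 = 158, setting it to 2.706 gives F = 5.466, and P(F on 1 and 158 df > 5.466) = 0.021.

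**Step 3: treatment random, seven visits, no patient term.** d = 2 × 80 × 7 − 8 = 1112, and the cut-off becomes F = 5.401. Ignoring the correlation inflates F by the design effect 1 + 6ρ, so the error rate is P(χ² on 1 df > 5.401/(1 + 6ρ)).

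**Step 4: treatment fixed, still no patient term.** The same formula with 3.841 in place of 5.401.

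**Step 5: add a patient intercept.** The test then uses patient means, on 1 and 158 df. These rates come from 20,000 simulated null trials per ρ.

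| Model over seven visits | ρ = 0.3 | ρ = 0.5 | ρ = 0.7 |
|---|---|---|---|
| Design effect 1 + 6ρ | 2.8 | 4.0 | 5.2 |
| Treatment random, no patient term | 0.165 | 0.245 | 0.308 |
| Treatment fixed, no patient term | 0.241 | 0.327 | 0.390 |
| Treatment random, patient intercept | 0.019 | 0.020 | 0.022 |
| Treatment fixed, patient intercept | 0.048 | 0.049 | 0.050 |

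Simulation of the two rows without a patient term gave 0.165, 0.249, 0.306 and 0.240, 0.330, 0.391, in agreement with the formulas. At 100 per arm these rows were 0.164, 0.241, 0.306 and 0.238, 0.328, 0.384, so the target size does not change the picture.

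**Step 6: the fixed month-12 contrast.** In a separate simulation (100 per arm, ρ = 0.5, 4,000 runs), a plain comparison of the arms at month 12 rejected in 4.7% of trials with no effect and 87.9% with a one-unit effect. With treatment random and no patient term, the treatment variance was estimated as exactly zero in 38.5% of the null trials.

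**The case against.** The strongest reply is that the intention is clear. The plan names month 12 in the primary outcome and in hypothesis 1, compares groups at follow-up time points, tests a null of similarity two-sided, and sizes on a mean difference. The method's name, its missing-at-random claim and the remark on correlation all suggest that within-patient correlation will be modelled. On that view the high error rates belong to a model nobody would fit, and the 0.02 belongs to a test the plan never mentions.

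Much of this stands as a limit on the figures: they are conditional illustrations, not forecasts. It does not rescue the text. The wording occurs three times and is never corrected. Swapping the two labels would make time random and still leave no patient term and no month-12 contrast. Naming month 12 as the outcome does not put a month-12 parameter in the model.

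It can also be said that, in the Analytic Plan, the sentence follows hypothesis 2, so the primary test might be a separate one. In that case the primary hypothesis has no stated model at all, and the seven-visit figures would not apply to it. Either way the primary contrast is not supplied.

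A fair point remains about scope. A baseline covariate is good practice rather than a consequence of the random-treatment error, and covariates chosen by observed imbalance would still leave the model partly data-driven.

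**Conclusion.** The concern holds. The one model with stated terms is wrong as written for a two-arm comparison: it cannot estimate, as a parameter, the difference that hypothesis 1, the two-sided test and the sample size all require. It must be corrected before analysis, even if it is a slip.

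The possible effect on error is wide and has no single direction: from about 0.02 (treatment random, with a patient intercept or at a single time point) to 0.39 (treatment fixed, no patient term, ρ = 0.7), against a nominal 0.05. These values rest on the assumed correlations, complete data and, for random treatment, the assumed likelihood-ratio test. The inflated values arise only if no within-patient term is fitted. The first part of the conclusion, that no fixed arm difference exists in the model, needs none of these assumptions. The figures of 80 and 100 per arm are sound for a fixed contrast and need no change.

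**What to change.** Replace the sentence under Specific Aim 1 and in both places in the Analytic Plan with wording such as:

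> Linear mixed model for repeated measures of change from baseline, with treatment, visit (categorical) and treatment-by-visit as fixed effects, the baseline value of the outcome as a covariate, and within-patient correlation modelled by a patient random effect or a specified within-patient covariance. The primary result is the treatment difference at month 12 with its 95% confidence interval and two-sided p-value.

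State explicitly that this model serves hypothesis 1. Use it also for the other repeated continuous outcomes the sentence covers: pain interference, function, depression and anxiety. Say that it is the final regression model to which the covariate-adjustment statement refers. The covariance structure is the trial statistician's choice, but it should be named in advance. Both corrections are needed, because making treatment fixed without a within-patient term leaves the error at 0.24 or more under the assumptions above.

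The cost is wording only: same data, same SAS software, same sample size.

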1. Trial period: One to two percutaneous leads are inserted into the epidural space. The distal ends of the leads connect to an external pulse generator (outside the body) that delivers pulses of electricity to dorsal column of spinal cord. The patients live with this trial system for 5-10 days, testing its efficacy in reducing pain intensity and improving function. At the end of trial period, the physician removes the trial leads and discusses the outcome and further steps with the patient. The figure shows a trial system.
2. Implant of permanent device: If the patients experience more than 50% pain relief during trial period, they will undergo a surgery for implanting a permanent device. The permanent device consists of one to two epidural leads and an internal pulse generator. Patient can use a remote control to change between the programs of the device. They can also recharge the batter of the internal pulse generator. The figures show the components of spinal cord stimulator.

Traditional tonic spinal cord stimulation was the only available option for a few decades prior to introduction of newer waveforms in 2015 and 2016. Tonic stimulation delivers one pulse of electricity at frequency of 40-60 hertz. The pulse

width ranges from 200 to 450 microseconds. Patients usually need pulse amplitude of 3.5-8.5 milliamperes. High frequency stimulation increases the frequency to 10,000 hertz and the pulse width is limited to 30 microseconds. The patients usually need amplitudes of 1.5-3.5 milliamperes. High frequency spinal cord stimulation results in more than 50% pain relief in about three quarters of the patients (vs. half of the patients with tonic stimulation).^{4,5} Burst stimulation applies a train of five stacked pulses (without time to discharge between pulses) which is repeated at frequency of 40-60 Hertz. Burst spinal cord stimulation results in more than 50% pain relief in two third of patients.⁶ The figure compares tonic and burst waveforms.

In addition to somatic pain pathway (lateral thalamic pathway), burst spinal cord stimulation also activates medial thalamic pathway as detected by increased EEG activation.¹⁶ This pathway interprets emotional aspects of pain. Thus, clinicians have speculated that this waveform can improve patients' emotional status and mood; however, this is not verified in any clinical studies.

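### Comparing mood between waveforms within 12-month pain responders and non-responders is not a randomised comparison, and both the responder rule and the Aim 2 hypothesis are stated in conflicting ways

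*Combined protocol and SAP*

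**What the plan says.** Specific Aim 2 compares change in depression and anxiety between arms at 12 months. It then repeats the comparison in "responders (patients with 50% or more pain reduction at 1 year") and in non-responders, and gives the reason: "this analysis is to assess if pain reduction is an effect measure modifier in this relationship".

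Hypothesis 3 of the Analytic Plan first remarks, "Some improvement in depression and anxiety is expected to be the result of improvement in pain and function". It then says the investigators will also "perform a stratified analysis in responders (patients who achieve >50% pain relief) and non-responders (patients who do not achieve 50% pain relief"). No time point is attached to response there.

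Three other statements bear on this:

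- **Timing.** The High Frequency and Burst sections schedule the trial system after randomisation, so pain response is a post-randomisation outcome.
- **Expected arm difference in pain.** Hypothesis 1 reads "High frequency spinal cord stimulation is more effective than burst spinal cord stimulation in decreasing pain at 12 months". Background and Significance says high frequency "results in more than 50% pain relief in about three quarters of the patients", and "Burst spinal cord stimulation results in more than 50% pain relief in two third of patients".
- **Direction for mood.** Specific Aim 2 hypothesises that "high frequency spinal cord stimulation is more effective than burst spinal cord stimulation in decreasing stress and anxiety". Study Design and hypothesis 3 name burst as the better waveform for depression and anxiety.

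For the responder split, the plan gives no mediation or principal-stratum method, no adjustment for common causes of pain response and mood, no interaction test and no caveat. The only general adjustment is for baseline variables found to differ between arms.

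**The concern.** Randomisation balances the arms as a whole. It does not balance the subset of each arm that ends up with good pain relief. If one waveform relieves pain in more patients, its responders include some who would not have responded to the other, so the two responder groups contain different kinds of patients. The same applies to non-responders.

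Two mechanisms then act in opposite directions. Suppose high frequency yields more responders.

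- If unmeasured patient factors drive both pain and mood, selection makes burst look better in both strata.
- If pain relief itself improves mood, high frequency looks better in both strata, because relief still differs by arm inside each stratum.

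The remark that precedes the split in hypothesis 3 invites a reader to take a within-stratum difference as a waveform effect on mood beyond pain relief. That difference can be non-zero when no such effect exists. Calling it effect modification does not help, since a variable affected by treatment is not a valid modifier of a randomised contrast.

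Separately, the conflicting cut-off and hypothesis leave open who belongs in which stratum and what Aim 2 predicts.

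**Working it through.** **1. The plan's own figures.** From Sample size (SD 2.25, difference 1 NRS unit, two-sided 0.05, 80% power): n = 2 × (1.96 + 0.8416)² × 2.25² / 1² = 79.5, so 80 per group; 80 / 0.8 = 100 per arm. Both reproduce. They size the pain comparison, not the mood strata.

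**2. Stratum sizes.** Applying the Background rates to 100 per arm gives 75 versus 67 responders and 25 versus 33 non-responders.

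**3. Bias by hand, with no pain-independent waveform effect.** Assume a normal latent relief index L = z(p) + e, with response when L > 0. The mean of e is φ(z)/p in responders and -φ(z)/(1-p) in non-responders.

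- High frequency, p = 0.75: z = 0.674, φ = 0.318, means 0.424 and -1.271.
- Burst, p = 2/3: z = 0.431, φ = 0.364, means 0.545 and -1.091.
- Burst minus high frequency: 0.122 in responders, 0.180 in non-responders.

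A shared factor that gives correlation 0.5 between relief and mood produces 0.5 × 0.122 = 0.06 SD and 0.5 × 0.180 = 0.09 SD in favour of burst.

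With no shared factor, but mood improving 0.3 SD per unit of L, the remaining gap in L matters. It is (0.674 + 0.424) - (0.431 + 0.545) = 0.122 in responders and (0.674 - 1.271) - (0.431 - 1.091) = 0.063 in non-responders. That gives 0.04 and 0.02 SD in favour of high frequency.

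**4. Bias on the NRS, by simulation.** Assumed: whole-number NRS, baseline mean 7 and SD 1.5, SD of change 2.25, mood SD 8, no pain-independent waveform effect. The shared factor loads equally on pain change and mood, so their correlation is the loading squared. Response is at least 50% relief. Contrasts are mood score, high frequency minus burst, in points; positive favours burst.

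| Response, high frequency vs burst | Loading | Mood points per NRS point of relief | Responders | Non-responders |
|---|---|---|---|---|
| 54% vs 38% (falls of 3.5 vs 2.5) | 0.3 | 0 | +0.18 | +0.18 |
| | 0.5 | 0 | +0.52 | +0.49 |
| | 0.7 | 0 | +1.02 | +0.95 |
| | 0 | 1 | -0.32 | -0.43 |
| 75% vs 67% (falls of 4.85 vs 4.27) | 0.3 | 0 | +0.07 | +0.14 |
| | 0.5 | 0 | +0.22 | +0.35 |
| | 0.7 | 0 | +0.44 | +0.68 |
| | 0 | 1 | -0.21 | -0.18 |

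The all-patient contrast is about 0 when pain does not act on mood. If burst has the higher response rate at the 75%/67% setting, the range is -0.67 to +0.21. With equal response rates (70% in each arm), the step 3 model shows no bias.

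**5. Precision.** For 25 versus 33 non-responders the 95% half-width is 1.96 × 8 × √(1/25 + 1/33) = 4.16 points. The largest bias at 75% versus 67% is 0.68 / (4.16/1.96) = 0.32 standard errors.

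**6. Exactly 50% relief.** A fall from 8 to 4 is a response under Specific Aim 2. Under hypothesis 3 it neither exceeds 50% nor fails to achieve it, so it belongs to neither stratum. In the simulation about 8% of patients fall there at a baseline SD of 1 to 2, about 5% at 0.5, and none if everyone starts at 7.

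**7. Hypothesis.** Specific Aim 2 names high frequency, with stress and anxiety. Study Design and hypothesis 3 name burst, with depression and anxiety. Stress is not among the listed outcomes.

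**The case against.** **The split is supplementary, and the documents never claim a pain-independent effect.** Both are true. Mood is compared in all patients first, and modified intention-to-treat is the primary basis. But the stated purpose, effect modification, is not met by this split either, and no sentence says that the Aim 2 conclusion ignores it.

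**The bias is small.** This stands at the Background rates: 0.32 standard errors raises a 5% error rate to about 6%. At 54% versus 38% with the strongest loading, the responder contrast of 1.02 against a standard error of 8 × √(1/54.3 + 1/37.7) = 1.70 gives about 9%. At an assumed 80% versus 60% with correlation 0.5, the step 3 model gives 0.15 and 0.21 SD, with rejection in about 15% and 14% of simulated trials. Imprecision is the larger limitation in practice. Neither point makes the contrast interpretable.

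**The stratum sizes are uncertain.** This is fair. Background does not give the denominator of its rates. If they apply only to an assumed 80% implanted, and failed trials count as non-responders, that stratum is 20 + 80 × 0.25 = 40 versus 20 + 80 × 0.333 = 47, and the half-width is about 3.4. The conclusion is the same.

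**The cut-off conflict is editorial.** In part. The missing time point in hypothesis 3 can be filled from Specific Aim 2, and failing to achieve 50% can be read as placing exactly 50% among responders. The greater-than sign still contradicts that reading.

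**Direction does not matter under two-sided testing.** No test changes, and the rationale about the medial thalamic pathway beside the Aim 2 hypothesis suggests a drafting slip. It is a separate defect from the split, but the published hypothesis should still be unambiguous.

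**Conclusion.** The concern holds. By the plan's own expectations, the responder strata are formed after randomisation on a variable that the treatments affect differently. The within-stratum mood contrasts therefore identify neither effect modification nor a waveform effect separate from pain. At the plan's cited response rates the spurious difference is under 0.1 SD of mood (0.68 / 8 = 0.085), and at 54% versus 38% it is under 0.15 SD (1.02 / 8 = 0.13). It exceeds that only with a wider gap in response. These sizes and their sign rest on the assumed loading, pain-to-mood slope and SDs. The non-identification does not.

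The two textual conflicts, on the responder cut-off and on the direction and outcomes of the Aim 2 hypothesis, stand on the wording alone. The primary endpoint and the overall mood comparison are unaffected, so this should be corrected before analysis but does not threaten the trial.

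**What to change.** 1. State that the Aim 2 conclusion rests on the depression and anxiety comparison in all modified intention-to-treat patients.
2. Label the responder and non-responder results descriptive, with no between-arm tests and no claim of effect modification. Assess effect modification by baseline variables only; the depression and anxiety subgroups already planned are of this kind.
3. Use one responder definition and one time point in Specific Aim 2 and the Analytic Plan, placing exactly 50% relief in one stratum.
4. Reconcile the Aim 2 hypothesis with Study Design and hypothesis 3, in direction and in the outcomes named.
5. Optional: if the role of pain relief in mood is of real interest, add an exploratory mediation analysis using pain change at 3 or 6 months, adjusted for baseline pain, depression and anxiety. State its untestable assumption of no unmeasured confounding, since the same shared factor can bias it.

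Items 1 to 4 are wording changes and need no new data or patients. Their cost is the loss of a formal within-responder test. Item 5 is a new analysis and would remain exploratory.
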